Annual reporting will be conducted in compliance with TASC SOP 15: Preparing and Submitting Progress and Safety Reports in CTIMPs and Non-CTIMPs, as a condition of sponsorship and as a condition of a favourable opinion from a REC. An HRA Annual Progress Report for NCTIMPs will be prepared and submitted by the CI to REC, and copied to the Sponsor, on the anniversary date of the REC favourable opinion.

Any safety reports additional to SAE reports, for example, reports of a DMC, will be sent by the CI to REC, with a Safety Report Form, and to the Sponsor.

STUDY CONDUCT RESPONSIBILITIES

Protocol amendments and breaches

The CI will seek approval for any amendments to the Protocol or other study documents from the Sponsor, REC and NHS R&D Office(s). Amendments to the protocol or other study docs will not be implemented without these approvals.

If this necessitates a subsequent protocol amendment, this will be submitted to the Sponsor for approval and then to the appropriate REC and lead NHS R&D Office for review and approval.

In the event that a breach of GCP or protocol is suspected, this will be reported to the Sponsor Governance Office immediately.

Study Record Retention

Archiving of study documents will be in secure storage for 15 years after end of study.

End of Study

The end of study is defined as last patient last visit (LPLV). The Sponsor and CI have the right at any time to terminate the study for clinical or administrative reasons.

Mechanistic Insights into changes in peripheral blood flow following intermittent negative pressure.

The end of the study will be reported to the Sponsor and REC within 90 days, or 15 days if the study is terminated prematurely. The CI will ensure that any appropriate follow up is arranged for all participants.

A summary report of the study will be provided to the Sponsor and REC within 1 year of the end of the study.

Mechanistic Insights into changes in peripheral blood flow following intermittent negative pressure.

REPORTING, PUBLICATIONS AND NOTIFICATION OF RESULTS

Authorship Policy

The co-applicants will form the core authorship group. Ownership of the data arising from this study resides with the study team and their respective employer. On completion of the study, the study data will be analysed and tabulated, and a clinical study report will be prepared.

Publications

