Two groups will be evaluated in this PhD study – healthy volunteers and PAD patients (figure 1). This will be a single-blinded placebo controlled cohort study. All healthy volunteers will receive active -40mmHg

Mechanistic Insights into changes in peripheral blood flow following intermittent negative pressure.

INP while PAD patients will receive either an active device (-40mmHg INP) or placebo device (-10mmHg INP).

Randomisation

This will be a single-blinded study. The patients will not know whether they have been assigned to the active or placebo device. The researcher will know which device a patient has been assigned to. 80 PAD patients will be recruited in total. The first 20 PAD patients will not be randomised and will be assigned the active device. The subsequent 60 PAD patients will be randomised on a 2:1 basis with 40 patients assigned the active device and 20 assigned placebo. This will allow for more mechanistic studies to be carried out on patients receiving active -40mmHg INP. Patients will be randomised to either active or placebo using an online randomisation programme.

Patients will be told which device they were assigned to at the end of the study.

At the start of the study, eligible patients with an ABPI <0.9 will be approached in wards and clinics by the study team and vascular surgery team. Patients will be given an invitation letter along with an information sheet and reply slip. The study team will offer the patients INP and the patients will be trained to use the Flow-Ox themselves.

Group 1. 40 healthy subjects will be approached by e-mail and posters at Ninewells. Healthy volunteers will be studied to explore the effects of acute application (1 session) and repeated application (daily for up to 5 days) of INP on measurements described above. Importantly for the purposes of this PhD project, this group of subjects will allow us to explore the mechanistic effects of INP on normal physiology.

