The extent of oxidative stress will be estimated by measuring reactive oxygen species (ROS) using 2',7'-dichlorodihydrofluorescein, malondialdehyde by an LC-MS assay, and reduced glutathione (GSH) and oxidised glutathione (GSSG) by a standard LC-MS assay.

The surplus blood samples will be stored for 15 years at -80°C in the department, Division of Systems Medicine at Ninewells Hospital, and will be registered with Tayside Biorepository.

Laser Doppler Imaging

Laser Doppler imaging (using the Moor Instrument FLPI system) will be used to measure microvascular endothelial functions and blood perfusion of the lower limbs and arm. This test will be a good measure of how the lower limb circulation changes after INP application and if any systemic changes in microcirculation occur in the arm. The laser will be mounted on an adjustable arm attached to a portable stand. This will be positioned 20-30 cm above the skin to capture the image. The camera records blood flow in the superficial microvessels (arterioles, venules and capillaries) up to 1mm deep in skin. Repeated scans will be obtained and the perfusion calculated in arbitrary units. The microvessels of the lower limb will be stimulated using iontophoresis of acetylcholine (ACh) and sodium nitroprusside (SNP) to assess endothelium-dependent and –independent mechanisms, respectively.

At each assessment, wounds will be photographed using the laser Doppler imager and measured using appropriate software (eg. Photoshop).

Mechanistic Insights into changes in peripheral blood flow following intermittent negative pressure.

Flow-Mediated Dilatation

This test assesses endothelial function of the macrocirculation of the (brachial artery) through flow mediated changes. This test involves using a high resolution ultrasound probe (5-8 MHz) to measure changes in the diameter of brachial artery following 5-minutes of ischaemia applied to the forearm using a blood pressure cuff inflated above systolic blood pressure (normally 200mmHg). The measurement of brachial artery diameter will be taken on three occasions; baseline, during occlusion and after deflation. This test is not anticipated to have any risk to the participants.

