Research blood samples will be obtained at the research site following informed consent and other study procedures such as laser imaging, arterial stiffness and ABPI. This usually will occur on the first day in the designated research department, Division of Systems Medicine at Ninewells Hospital), and on two follow-up visits, after 1 INP application and again after up to 5 days daily INP.

Mechanistic Insights into changes in peripheral blood flow following intermittent negative pressure.

DATA COLLECTION AND DATA MANAGEMENT

Data Collection

The patients will be given an identification number to ensure anonymity. Data collected will include gender, age, CHI number, previous medical history, medications, diagnosis, treatment, blood report findings, and personal history. This clinical data will be used in the analysis of results and will be used to correlate with the findings of the vascular assessments. The data will be collected by the research team on a paper Case Record Form (CRF), which will not hold any name or initials, with subsequent transcription into an Excel database. Electronic storage will be in an encrypted form on a University of Dundee password-protected device.

Study assessments will be conducted by the PI and a trained research member of the team under the supervision of the CI.

Data Management System

Data management will be conducted in compliance with TASC SOPs on Data Management, including TASC SOP53 Data Management Systems in Clinical Research. The data management system (DMS) will be EXCEL, as approved by Sponsor. The DMS will be based on the protocol and CRF for the study and individual requirements of the investigators. The CRF will collect only information that is required to meet the aims of the study and to ensure the eligibility and safety of the participant. The study database will be compliant with TASC SOP53 Data Management Systems in Clinical Research. The database is managed in line with all applicable principles of medical confidentiality and data laws. The Data Controller will be the University of Dundee and the Data Custodian will be the CI. The CI may delegate CRF completion but is responsible for completeness, plausibility, and consistency of the CRF. Any queries will be resolved by the CI or delegated member of the study team. Database lock will be conducted in compliance with TASC SOP32 Locking Clinical Study Databases.

Verifying data

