Data entry and checking will be undertaken by a single entry with a second look. The data entry and checking process will be decided according to risk. Data that is recorded in the CRF that is not source document in itself will be consistent with the source documents or the discrepancies explained. Checks will be made on all missing values and values out with normal or expected ranges and that values entered

Mechanistic Insights into changes in peripheral blood flow following intermittent negative pressure.

are of the correct type: i.e. numerical instead of text. Logical checks will be performed to ensure consistent reporting between relevant fields and that there are no differences between fields. Data checking will continue until all missing data and/or inconsistent values have been corrected or clarified. When data checking is complete, with no outstanding data queries, the database will be locked, using the Protect Worksheet function of EXCEL, as FINAL RESULTS. The EXCEL spreadsheet will remain archived on the Dundee University secure server for 5 years for the retention of essential documents, thereafter it will be deleted.

STATISTICS AND DATA ANALYSIS

Sample Size Calculation

As this is a PhD project exploring mechanisms of vascular changes, precise power calculations have not been obtained. The results from this PhD project will guide us regarding subsequent power calculations. However, based on our previous work exploring mechanisms of changes in vascular function using various interventions, n=25 subjects will provide at least 80% power and 5% significance to detect a 20% before and after difference within subjects in the vascular function markers proposed in this study.

Proposed Analyses

Changes in blood flow and endothelial function in the lower limbs using laser Doppler perfusion imaging and iontophoresis will be compared primarily within each group and also between patient groups at baseline, after 1 INP session and after the last INP (4 to 8 weeks) is applied. The primary outcome measure will be the change in peak blood flow response to acetylcholine and sodium nitroprusside.

Data will be analysed using widely available statistical analysis software such as SPSS. Analytical methods will include t-tests, chi-square, ANOVA, correlation and regression as appropriate.

Mechanistic Insights into changes in peripheral blood flow following intermittent negative pressure.

STUDY MANAGEMENT AND OVERSIGHT ARRANGEMENTS

Study Management

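### Nothing keeps arm and visit hidden from whoever reads the primary-outcome scans; coded reading within the existing team would reduce the reading part of the bias, but not the part that arises at capture

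*Combined protocol and SAP*

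**What the plan says.** - **Blinding (Study Design, Randomisation).** For patients: "The patients will not know whether they have been assigned to the active or placebo device". For staff: "The researcher will know which device a patient has been assigned to".
- **Who measures (Data Collection).** "Study assessments will be conducted by the PI and a trained research member of the team under the supervision of the CI". No section says that either assessor is unaware of the device, that device handling is kept apart from measurement, or that images are read under a code.
- **Primary outcome (Proposed Analyses).** "The primary outcome measure will be the change in peak blood flow response to acetylcholine and sodium nitroprusside".
- **How the scan is obtained (Laser Doppler Imaging).** The imager is on an adjustable arm: "This will be positioned 20-30 cm above the skin to capture the image". Then: "Repeated scans will be obtained and the perfusion calculated in arbitrary units". No rule is given for the region, for which scans count, or for what defines the peak.
- **Other image measures.** Brachial diameter is measured by ultrasound for FMD. Wounds are photographed at each assessment and sized in image software. Neither is the primary outcome.
- **Order of comparisons (Proposed Analyses).** Laser Doppler results "will be compared primarily within each group and also between patient groups at baseline" and at the later visits.
- **Allocation (Randomisation).** The first 20 PAD patients all get the active device without randomisation. The next 60 are randomised, 40 to active and 20 to placebo.

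**The concern.** Patient blinding protects against the patient's own expectations. It does nothing about the person who takes or reads the scan. That person may know the device, has no written rule for region, scan or peak, and works from a protocol whose FLOW-Ox System section already states that the placebo leaves blood flow unchanged. The path for a reading that leans in the expected direction is open.

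Two sets of results are exposed. A reader who knows the visit can shift the before-after changes, which the plan compares first. A reader who knows the arm can shift the active-placebo difference, which comes second but is the only randomised evidence in the study. A shift of this kind adds directly to the estimate and does not shrink as patients are added.

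**Working it through.** **1. The plan's own figure.** The Sample Size Calculation section states that n = 25 gives at least 80% power at 5% significance for a 20% within-subject change. It gives no SD of the change and does not say one- or two-sided, so the figure cannot be reproduced. It can be solved backwards for the SD at which power is exactly 80%:

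- Two-sided, normal: SD = 20 × √25 / (1.960 + 0.842) = 35.7 points.
- Two-sided, paired t with 24 df (noncentral t): SD = 34.2 points.
- One-sided: 40.2 (normal) or 39.1 (t).

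Because the plan says *at least* 80%, 34.2 is about the largest SD consistent with the claim under a two-sided t-test. It is not an estimate. The section also says that no precise power calculation was made. SD 20 to 50 is therefore shown as a range.

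**2. The randomised comparison, 40 v 20.** Assume the same SD in both arms.

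SE = SD × √(1/40 + 1/20). At SD 34.2: 34.2 × 0.2739 = 9.4 points.

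If the true difference is zero and reading adds b points to active minus placebo, the two-sided 5% test rejects at the rate of a noncentral t with 58 df and noncentrality b/SE. The values of b are assumptions; the documents give none.

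| Shift b (points) | SD 20 (SE 5.5) | SD 34.2 (SE 9.4) | SD 50 (SE 13.7) |
|---|---|---|---|
| 0 | 5.0% | 5.0% | 5.0% |
| 2 | 6.5% | 5.5% | 5.2% |
| 5 | 14.6% | 8.2% | 6.5% |
| 10 | 43.5% | 18.2% | 11.1% |
| 15 | 76.8% | 35.0% | 19.0% |

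**3. The within-group changes.** The same argument applies with noncentrality b × √n / SD and n − 1 df. At SD 34.2, a 10-point before-after shift gives a false-positive rate of 28.9% at n = 25. With all 60 active patients the rate is about 60%: a fixed bias becomes easier to mistake for an effect as n grows.

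**4. What coded reading can remove.** It acts on choices made at reading (region, scan, peak). It cannot act on what happens at the visit: imager position, iontophoresis, the decision to repeat a scan. For a total bias of 10 points at SD 34.2 in the 40 v 20 comparison:

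| Share arising at capture | Bias left after coded reading | False-positive rate |
|---|---|---|
| 100% | 10 points | 18.2% |
| 75% | 7.5 points | 12.3% |
| 50% | 5 points | 8.2% |
| 25% | 2.5 points | 5.8% |
| 0% | 0 points | 5.0% |

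The documents do not say how the bias would divide between capture and reading.

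**The case against.** Single-blinding is a disclosed choice in an exploratory PhD study, and the between-group comparison is not the leading one. Both points are correct. They do not answer the concern, because the within-group changes are open to the same bias when the reader knows the visit, and because reading can be masked without changing the single-blind design.

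The figures rest on an SD inferred from a loose power statement and on shifts with no source. That stands: they show what a shift of a given size would do, not that one will occur.

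A reader might go further in three ways that the documents do not support:

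- *That coded reading removes most of the bias.* This holds only if more than half of it arises at reading. No section gives that split, and the scan operator would still know the device.
- *That the protocol says the measures are operator-dependent and read from stored images.* Storage before measurement is described only for wounds. For laser Doppler the protocol says that scans are obtained and perfusion calculated; for FMD, that diameter is measured on three occasions. Reader choice of region or edge, and reading away from the visit, are reasonable inferences but remain inferences.
- *That two named assessors already amount to a masked reader.* The protocol does not say that either is unaware of allocation or absent from the scan. Masking works only if one codes, the other reads, and the reader did not take that scan.

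**Conclusion.** The concern holds in this limited form. The researcher knows the device, no masked reading is described, and the primary outcome is calculated from scans with no written reading rules. Observer bias can therefore enter the primary within-group changes and the secondary randomised comparison.

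Its size is unknown. Under the assumptions shown (equal SD in both arms, an additive shift, a two-sided 5% test), a 10-point shift would turn a 5% false-positive rate in the 40 v 20 comparison into 18% at SD 34, and into 43% to 11% over SD 20 to 50. The documents do not show that bias will occur, and single-blinding is not in itself an error. They also do not state whether the baseline scan precedes randomisation, so whether baseline readings are protected from knowledge of the arm cannot be determined.

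This is a cheap improvement worth making, not a reason to hold the study.

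**What to change.** Keep the single-blind design and add a paragraph to the protocol:

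1. Save laser Doppler scans, and FMD and wound images where these are stored, under a random code that hides patient, arm and visit.
2. Fix the rules for region, scan selection and peak before any reading.
3. Have one existing team member code the files and the other read them in batches. The reader of a file must not have taken that scan.
4. Break the code only after the readings are locked. Study Design (Group 2) uses the initial 4-week results to decide how many patients are tested for 8 weeks, so read and lock those data as a separate batch; otherwise the masking would conflict with that use.
5. State that bias at capture remains while the operator knows the device.

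**Cost:** time to code files, and readings that come in batches rather than at once. No new visits are needed. No new staff are needed provided that, for each scan, one of the two assessors was not the operator.

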Group 2. 80 patients with PAD will be recruited from in-ward patients and from outpatient vascular clinics. Patients will be recruited by the Vascular Surgery team lead by the Consultant Vascular Surgeon who is the second Academic Supervisor of the PhD student. Patients will be randomised to active INP device (-40mmHg) or placebo INP device (-10mmHg). 20 patients in total will receive the placebo device and 60 will receive the active device. The effects of INP on the measurements described above will be made at baseline (before application of INP), following 1 session of INP (acute effects) and following 4-8 weeks of daily INP. As this is a PhD project, not all patients will undergo 8 weeks' of INP. Based on the initial studies of the shorter 4-week duration, we will be able to examine how many patients will be tested for 8 weeks.

Mechanistic Insights into changes in peripheral blood flow following intermittent negative pressure.

Before application of INP, anthropometric baseline measurements (height, weight) will be taken from all participants at Level 7, Division of Systems Medicine, Ninewells Hospital. For patients, medical notes will be reviewed for clinical characteristic including information on past medical history, drug therapy and blood biochemistry.

[figure not shown]

Figure 1:Flow Chart of study design and measurement techniques.

FLOW-Ox System:

Application of INP will be made using the Flow-Ox machine, a CE marked device provided by Otivio as a gift (Otvio AS, Oslo, Norway) (Figure 1). Participants will be asked to be comfortably clothed and seated (with a 130-degree angle between their hip and knee joint) for 20 minutes prior to the start of the experiment. They will be asked to place a leg into the Flow-Ox chamber which is a molded polyethylene

Mechanistic Insights into changes in peripheral blood flow following intermittent negative pressure.

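### The plan does not say which PAD patients enter the active–placebo comparison; as written it allows 60 vs 20, with a third of the active arm never randomised

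*Combined protocol and SAP*

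**What the plan says.** Under Study Design, Randomisation, the assignment rule has two stages. First: "The first 20 PAD patients will not be randomised and will be assigned the active device". Then: "The subsequent 60 PAD patients will be randomised on a 2:1 basis with 40 patients assigned the active device and 20 assigned placebo". The reason given is to have more active-device patients for mechanistic work. No rule for analysing the two stages follows.

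The Group 2 paragraph of the same section does not mention the first stage. It says "Patients will be randomised to active INP device (-40mmHg) or placebo INP device (-10mmHg" and gives the totals: "20 patients in total will receive the placebo device and 60 will receive the active device".

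Proposed Analyses covers blood flow and endothelial function and describes the planned comparisons as follows: "primarily within each group and also between patient groups at baseline, after 1 INP session and after the last INP (4 to 8 weeks". It does not define patient groups and names no analysis set. On method it says only: "Analytical methods will include t-tests, chi-square, ANOVA, correlation and regression as appropriate".

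The only groups that the text defines are healthy volunteers and PAD patients (Study Design: "Two groups will be evaluated in this PhD study"). Healthy volunteers are followed up "after 1 INP application and again after up to 5 days daily INP" (Study & Safety Assessments), so they have no 4-to-8-week visit. At that timepoint the natural reading of a between-group comparison is active versus placebo among PAD patients. That reading is inferred; the plan does not state it.

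**The concern.** Active versus placebo is the only between-device comparison in PAD patients, and the study is described as placebo controlled. Randomisation protects the 40 vs 20 comparison. It does not protect the first 20, whose device is fixed before they enrol and who have no placebo patients recruited alongside them. If they enter the active arm, any difference between early and later patients enters the device estimate. It cannot be separated from a device effect, because there is no early placebo patient to compare with.

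The documents report no such difference, but two features of the design make one possible. The researcher knows each patient's device. Also, the Group 2 paragraph lets the initial 4-week studies decide how many patients go on to 8 weeks, while Proposed Analyses treats 4 to 8 weeks as a single timepoint. If those initial studies include the first 20 (the text does not say), a pooled active arm would hold relatively more 4-week patients than the placebo arm.

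Because the choice is open, an analyst could run 60 vs 20, 40 vs 20 or both, and comply with the plan each time.

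**Working it through.** **Head counts (Randomisation and Group 2).** Active: 20 + 40 = 60. Placebo: 20. Total: 60 + 20 = 80. The two paragraphs agree on totals and differ on who is randomised (60 of 80 against no stated exception). Non-randomised share of a pooled active arm: 20/60 = 1/3.

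**Bias.** Let the first 20 differ from later active patients by d, in SD of the change score. The pooled active mean shifts by (20 × d + 40 × 0)/60 = d/3. The documents give no value for d, so a range is assumed.

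**Type I error.** No device effect, two-sided 5% pooled-variance t-test, 400,000 simulated trials per value of d:

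| d (SD) | Bias of 60 vs 20 (SD) | Type I error, 60 vs 20 | Type I error, 40 vs 20 |
|---|---|---|---|
| 0 | 0 | 5.0% | 5.0% |
| 0.25 | 0.08 | 6.0% | 5.0% |
| 0.5 | 0.17 | 9.1% | 5.0% |
| 0.75 | 0.25 | 13.8% | 5.0% |
| 1.0 | 0.33 | 20.1% | 5.0% |

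A normal approximation that holds the residual SD fixed gives 6.2%, 9.9%, 16.2% and 25.2% for the four non-zero shifts. The simulated figures are lower because the shift also spreads the pooled active arm: it adds about (20 × 40/60)d²/78 = 0.17d² to the estimated variance.

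**Shift in the opposite direction.** True effect 0.78 SD, chosen to give 40 vs 20 a power of 80%:

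| d (SD) | Power, 60 vs 20 | Power, 40 vs 20 |
|---|---|---|
| 0 | 85% | 80% |
| -0.25 | 76% | 80% |
| -0.5 | 63% | 80% |
| -0.75 | 49% | 80% |
| -1.0 | 34% | 80% |

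**Where pooling stops paying.** Mean squared errors are equal when (d/3)² + 1/60 + 1/20 = 1/40 + 1/20, so |d| = 3 × √(1/40 − 1/60) = 0.274 SD. Below this, 60 vs 20 has the smaller mean squared error; above it, the larger.

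**Precision given up by using 40 vs 20.**
- Standard error, 60 vs 20: √(1/60 + 1/20) = 0.258 SD.
- Standard error, 40 vs 20: √(1/40 + 1/20) = 0.274 SD. The ratio is 1.061.
- Detectable difference at 80% power (noncentral t): 0.73 SD for 60 vs 20 (78 df) and 0.78 SD for 40 vs 20 (58 df).
- Regression on all 80 with device and cohort terms and no other covariates: the device coefficient equals the 40 vs 20 difference in means exactly. The standard error factor is again 0.274; with 77 residual df the detectable difference is 0.777 SD, against 0.780.

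**Power on the plan's own scale.** Sample Size Calculation claims at least 80% power with n = 25 for a 20% within-subject difference. It gives no SD, so the claim cannot be reproduced. Reading it as a two-sided paired t-test for a 20-point change, the implied SD is 34.2 if power is exactly 80% and 29.6 if it is 90%. Carrying that SD to both arms and assuming a 20-point between-arm difference:

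| Assumed SD | 60 vs 20 | 40 vs 20 | All 80 with cohort term |
|---|---|---|---|
| 34.2 | 61% | 55% | 56% |
| 29.6 | 73% | 68% | 68% |

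The loss is about 5 percentage points in both cases.

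**The case against.** The strongest reply is that this is a gap and not an error. Proposed Analyses never states a 60 vs 20 test. Its wording equally allows 40 vs 20 or a cohort term, and the meaning of patient groups has to be inferred. Figure 1, the study flow chart, is not shown in the text available and might present the first 20 as a separate stream. The comparison is second to the within-group one, the study is exploratory without precise power calculations, and the FLOW-Ox System section offers another control, the untreated leg. Every bias figure depends on an assumed d. The largest need a full 1.0 SD shift between consecutive patients at one centre under the same criteria, and for small shifts pooling is the more accurate choice. The Randomisation paragraph states the rule plainly, so a reader of both paragraphs is unlikely to be misled about who is randomised.

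Much of this stands, and it limits the weight of the point. It does not close the gap. The untreated leg does not compare active with placebo, and it is not a clean control if the effect is systemic, which the secondary objectives set out to test. Whether d is small cannot be learned for placebo patients, since none is enrolled early. The arms are presented as 60 and 20, so the pooled analysis is the one a reader would most easily run.

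**Conclusion.** The concern holds and should be fixed before analysis. The plan leaves the active–placebo analysis set open and presents arms of which one third of the active side was never randomised. The potential bias is one third of any early–late shift: 0.08 to 0.33 SD for assumed shifts of 0.25 to 1.0 SD, with type I error of about 6% to 20% in place of 5%, or a matching loss of power if the shift runs the other way. These sizes are conditional, because the documents neither report nor rule out a shift. The conclusion also assumes that the between-group comparison at 4 to 8 weeks means active versus placebo. The comparison is secondary, the within-group analyses are untouched, and the study is not invalidated.

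**What to change.** In Proposed Analyses:
- Define patient groups, and state that active-versus-placebo comparisons use only the 60 randomised patients (40 vs 20).
- Report the first 20 as a separate, non-randomised active cohort. They can still join the other 40 active patients in within-patient mechanistic analyses, which is the purpose given for the extra active patients.
- Show any 60 vs 20 result only as a labelled sensitivity analysis.
- If all 80 enter one regression, include a cohort term.

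In the Group 2 paragraph, reconcile the description of who is randomised with the Randomisation section. If Figure 1 bears on this, align it too.

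The change is to wording only, with no effect on recruitment or visits. Under Protocol amendments and breaches it needs Sponsor, REC and NHS R&D approval before use. The statistical price is the 6% wider standard error and the roughly 5 points of power shown above; the power figure is illustrative, because the documents give no SD.
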